4.4 Early Withdrawal of Subjects

Any subject may discontinue participation in the study for any reason at any time. Subjects who elect to withdraw may resume other treatments as determined appropriate by their physician. Reasons and circumstances surrounding withdrawal will be documented in the study records.

When a pregnancy has been confirmed in a subject during maternal exposure to treatment, the study drug will be discontinued immediately and the subject will be referred to her primary physician. In the event that any subject discontinues study drug and, subsequently, withdraws from the study before completion, regardless of reason, reasonable efforts will be made to have the subject return for an early termination visit and have the end of treatment procedures completed. If a subject is unable to return to the clinic for an early termination visit, attempts will be made to contact the subject by phone to assess AEs. Subjects will be asked to return to the clinic for further assessments if the PI deems it appropriate.

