4.6 Data Collection for Withdrawn Subjects

Data of withdrawn subjects will be collected up to the point of withdrawal. This data will still be included in the pooled data of the study for further analysis. For subjects who withdraw from further data collection, there will not be replacement with more subjects. When study drug is discontinued (regardless of the reason), the investigator will encourage that all of the evaluations required at the End of Treatment Visit be performed and that any additional evaluations be completed that may be necessary to ensure that the patient is free of untoward effects. The patient will be encouraged to seek appropriate follow-up for any continuing health problems.

5 Study Drug

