5.2.1 Dose Adjustment

Dose of Entresto is started at the middle level of 49/51 mg twice-daily and if well tolerated by the patient then dosage is increased to the target maintenance dose described above. If manifestations of side effects of Entresto appear (Table 1), dose can be lowered to the lowest dose of 24/26 mg twice-daily. If at the lowest dose level adverse events continue then patient will be withdrawn from the study. Dose of Entresto will be administered following the recommendation as written in the Entresto prescribing information sheet from Novartis Pharmaceuticals Corporation East Hanover, New Jersey 07936 as revised by the FDA on August, 2015 (Patient information sheet attached). The study physician [name] will be responsible for all dose changes in subjects participating in this study. Specific guidelines on dosage change are detailed below.

Dosage modifications guidelines:

Any patient with a serum potassium > 5.2 mEq/L after randomization requires regular, repeated checks of potassium concentration (beyond that prescribed in the protocol) until it is clear that the potassium concentration is stable and not rising into the range of concern (≥ 5.5 and < 6.0 mEq/L) or potential danger (≥ 6.0 mEq/L).

Corrective action for management of hyperkalemia.

Serum potassium > 5.2 and less than or equal to 5.5 mEq/L

- Confirm potassium concentration in a non-hemolyzed sample.
- Reinforce low potassium diet and restriction of food/drinks with high potassium content (e.g. orange juice, melon, bananas, low-salt substitutes etc.).
- Review medical regimen (including dietary supplements and over-the-counter medications) for agents known to cause hyperkalemia. Consider reduction in dose or discontinuation of these agents:
 - Potassium supplements, e.g., potassium chloride.
 - Salt substitutes.
 - Non-steroidal anti-inflammatory drugs (NSAIDs)
 - Herbal Supplements:
 - For example, Noni juice, alfalfa (*Medicago sativa*), dandelion (*Taraxacum officinale*), horsetail (*Equisetum arvense*), nettle (*Urtica dioica*), milkweed, lily of the valley, Siberian ginseng, hawthorn berries.
- Repeat serum potassium measurement within 3 to 5 days.
- If serum potassium remains > 5.2 and ≤ 5.5 mEq/L, regularly monitor serum potassium levels to ensure stability (suggested once monthly).
- Consider down-titration of study medication, according to study physician medical judgment.

Serum potassium > 5.5 and < 6.0 mEq/L

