9.1 Statistical Methods

General baseline characteristics will be described using mean and proportions. Smirnov-Kolmogorov tests will be used to test normality of distribution of variables. For variables that do not follow the normal distribution, log transformation will be performed. Linear simple and multiple regressions will be performed to assess

association between the effects of Entresto on metabolic and physiological changes with clinical functional variables. Differences between the placebo and the

Entresto group will be assessed using independent sample t-test and Chi-square for quantitative and categorical variables, respectively. Change following the 12 week clinical trial in metabolic and physiological parameters will be assessed using paired sample t-test. Repeated measures analysis of covariance will also be used to evaluate differences between groups as a function of time. A p value < 0.05 will be used to determine statistical significance. Effect size (EF) calculated as $EF = (\text{mean Entresto group} - \text{mean placebo}$

group)/SD (control group) will be used to assess the clinical significance of the effects of Entresto⁶³. The PI will be in charge of performing all statistical calculations using SAS v 9.3 by SAS Institute Inc., Cary, NC. [name] Jr. Professor at the School of Public Health a statistician with more the 800 publications will be a consultant in statistical analysis of the data.

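### Patients whose adverse events continue at the lowest dose leave the study, so their Week 12 walking outcomes are not secured and no analysis rule covers the gap

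*Combined protocol and SAP*

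**What the plan says.** Section 5.2.1 (Dose Adjustment) ends its step-down rule with: "If at the lowest dose level adverse events continue then patient will be withdrawn from the study". Other text stops or adjusts only the drug: the potassium and renal guidance later in section 5.2.1, and section 11.3 on serious adverse events.

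Section 4.6 says "Data of withdrawn subjects will be collected up to the point of withdrawal", that "This data will still be included in the pooled data of the study for further analysis", and that "there will not be replacement with more subjects". For drug discontinuation it adds that "the investigator will encourage that all of the evaluations required at the End of Treatment Visit be performed". Section 4.4 says that when a subject stops drug and then withdraws, whatever the reason, "reasonable efforts will be made to have the subject return for an early termination visit and have the end of treatment procedures completed". Neither section gives that visit a Week 12 date. Section 6.4 asks for the end-of-treatment return within 24 hours of the last pill.

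Section 6.2 and the Schedule of Events place no treadmill or 6 minute walk test at the clinic visits between baseline and Week 12.

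For the comparison of the arms, section 9.1 states that the "Entresto group will be assessed using independent sample t-test", and it also plans a repeated measures analysis of covariance. It names no analysis population and no method for missing outcomes. Section 9.2 makes no allowance for dropout.

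**The concern.** The primary objective in section 1.2 is the effect of 12 weeks of treatment on treadmill walking and the 6 minute walk. Under section 5.2.1 a patient who cannot tolerate the lowest dose leaves the study. That patient then has either no post-baseline walking value or one measured at whatever week dosing ended. The plan does not say whether such an early value is analysed beside true Week 12 values, analysed separately or left out.

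The loss would be related to tolerability, and tolerability may differ by arm. If the arms lose patients at different rates, and those patients would have changed less than the others, a comparison of completers is no longer a comparison of the groups as randomised. It would tend to favour the drug. With 15 patients per arm, two or three such patients move the mean noticeably.

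**Working it through.** **Do the other sections repair the gap?**

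- *Early termination visit (4.4, 4.6).* It may yield the treadmill test (Visit 6) and the 6 minute walk (Visit 7), and the data are kept. It depends on effort and encouragement and has no Week 12 date. Section 6.4 counts from the last pill, which points to testing at the time of stopping.
- *Repeated measures analysis (9.1).* It needs a post-baseline walking value. None is scheduled before Week 12, so a patient who leaves without an early test contributes nothing to the treatment contrast.
- *Replacement (4.6).* None.

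**Reproducing the plan's sample size (9.2).** Inputs: difference 278 m, SD 240 m, alpha 0.05, power 0.85, 15 per group. The 278 m is a pre-post change, which the plan uses as a between-group difference. Sidedness is not stated; a two-sided test reproduces the figure.

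- Standardised difference: 278/240 = 1.158.
- Normal formula: n = 2 × (1.960 + 1.036)² × (240/278)² = 13.4, so 14 per group.
- Exact noncentral t: power 0.839 at 14 per group and 0.865 at 15. Fifteen is the smallest number that reaches 0.85.

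**Power if active patients are lost and placebo is complete (assumption).** Noncentrality = 1.158 / √(1/n₁ + 1/15), with n₁ + 13 degrees of freedom.

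| Active patients lost | n₁ | Noncentrality | Power |
|---|---|---|---|
| 0 | 15 | 3.17 | 0.865 |
| 1 | 14 | 3.12 | 0.852 |
| 2 | 13 | 3.06 | 0.837 |
| 3 | 12 | 2.99 | 0.820 |

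**Bias of a completers-only active mean.** Let k of 15 active patients be lost, completers gain 278 m, and the lost patients would have gained g. The all-randomised mean is [278(15 − k) + gk]/15, so the overstatement is (k/15)(278 − g). The documents give neither k nor g; the values below are assumptions.

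| k | g = 0 | g = 139 m (half) | g = 278 m |
|---|---|---|---|
| 1 | 19 m | 9 m | 0 |
| 2 | 37 m | 19 m | 0 |
| 3 | 56 m | 28 m | 0 |

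The between-arm difference is overstated by the same number of metres only if the placebo mean is unaffected.

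**How likely are two or more losses?** If each active patient had a 5%, 10% or 20% chance of such a withdrawal (assumed), the binomial probability of at least two in 15 would be 17%, 45% or 83%.

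**The case against.** A reader might infer that Week 12 outcomes are certainly lost, and lost selectively from the active arm. The documents do not support that.

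- Sections 4.4 and 4.6 seek the end-of-treatment tests from patients who stop and keep what was collected, so a walking value may exist. What is not secured is the value at Week 12.
- The rule is applied blind to both arms. Section 5.5 provides placebo capsules at all three dose levels, with a blinded study physician giving them out.
- A reader might also multiply the Entresto rates in Table 2 by 15 (hypotension 15 × 0.18 = 2.7, hyperkalaemia 15 × 0.12 = 1.8) and take the results as expected losses. Those are event rates, not withdrawal rates, and section 5.2.1 sets monitoring and dose steps before withdrawal. They come from a heart failure trial against enalapril, and the comparison is mixed: hypotension 18% v 12%, hyperkalaemia 12% v 14%, renal failure 5% v 5%.
- The loss of power is small. One active loss leaves 0.852, still above 0.85.

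All of this stands and limits the claim. It does not remove it. Blinding makes the rule even-handed, but it does not make adverse events equally frequent. Section 5.2.1 calls the Table 1 triggers side effects of Entresto. The comparator is placebo, and current users of ACE inhibitors or ARBs are excluded, so the active arm receives an ARB (valsartan) that the placebo arm does not. More withdrawals on active drug are therefore probable, but their size cannot be derived. Equal numbers lost would still leave missing or mistimed outcomes with no stated handling.

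**Conclusion.** The point holds in a limited form. Section 5.2.1 merges stopping drug with leaving the study and does not sit well with sections 4.4, 4.6 and 11.3 or with its own later guidance. Followed as written, the plan leaves Week 12 walking outcomes missing or off schedule for patients who do not tolerate treatment. Neither the t-test nor the repeated measures analysis repairs this.

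The possible bias matters more than the lost power. Two or three active losses would overstate a completers-only active mean by 37 or 56 m, against an assumed effect of 278 m. That is an upper illustration: it takes lost patients to gain nothing, no early value to be used and, for the between-arm difference, no offsetting placebo losses. If lost patients would have gained half as much, the figures are 19 and 28 m; if they would have gained as much as completers, there is no bias. Power would fall from 0.865 to 0.837 or 0.820.

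**What to change.** 1. Reconcile section 5.2.1 with sections 4.4 and 4.6, so that stopping study drug and leaving the study are separate, separately recorded events.
2. Seek the treadmill and 6 minute walk tests at Week 12 from every randomised patient who still consents and can be safely tested, on or off drug. Adjust the timing in section 6.4, which now counts from the last pill.
3. In section 9.1, analyse all randomised patients in their assigned arm with adjustment for baseline. State in advance whether an early-termination value may ever stand in for Week 12.
4. Add a sensitivity analysis that assumes no improvement where Week 12 data are missing, and report withdrawals and missing walking tests by arm.

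The cost is protocol wording, one extra analysis, and asking a few off-drug patients to attend visits that are already scheduled. Those visits are not light: the schedule gives two of 4 hours each, although only the walking tests are essential here. Some patients may not be testable; Appendix A lists electrolyte abnormalities as a relative contraindication to exercise testing. The estimate becomes the effect of being assigned to the drug, which may be smaller than the effect in those who stay on it. No dosing or drug-stopping rule is changed or proposed.

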5.3 Method for Assigning Subjects to Treatment Groups

A variable block randomization design will be used to ensure a balance in sample size between the two groups

5.4 Subject Compliance Monitoring

Compliance to drug administration will be documented at all study visits. Subjects will be asked to bring in their medication at each study visit for monitoring purposes.

5.5 Blinding of Study Drug

Blinding of the drug will be done by the investigational Drug Services (IDS) at the University of Minnesota. Once a subject is eligible to participate in the study, the PI will inform IDS and they will

be in responsible for randomizing the subject into one of the two groups and preparing the first two weeks of treatment. Capsules containing pills with either placebo or Entresto will be placed in a container identified with a code, which will be kept by IDS pharmacy unless it is requested as part of an emergency response or study termination. Each individual pill will be packaged in identical capsules by IDS pharmacy staff. Entresto comes in pills of three dosages: 24/26 mg, 49/51mg and 97/103 mg. Capsules for each of the three dosages (placebo or Entresto) will be prepared by IDS and the study physician (blinded) will provide the capsules following the dosing procedures as described in 5.2.1. The subject will only be unblinded if there is a medical situation where it is necessary to know if the subject is on drug or placebo.

[figure not shown]
5.6 Receiving, Storing, Dispensing and Return

The Investigational Drug Services (IDS) pharmacy staff will in charge of preparing the pills and the placebo capsules and dispensing the drug for this study.

6 Study Procedures

6.1 Participant Timeline/Procedures

Screening and Baseline

Pre-Screening Phone Interview

An initial phone interview will be used to pre-screen subjects for potential eligibility. Subjects that meet all inclusion criteria and none of the exclusion criteria as described in 4.2, will be invited to participate in the study. If potential participants are interested,

they will be asked to come in to discuss the study further and if they wish to participate they will be asked to sign the consent form.

Visit 1 (Screening/Baseline 1)

After consent has been obtained, the following tests and procedures will be done to determine whether the potential subject is eligible to participate.

- Patients will be asked a series of questions about symptoms suggestive of intermittent claudication (IC)
- Brachial and ankle systolic blood pressure will be measured with both arms and legs. Patients will lie supine and will rest quietly for 5 minutes and systolic blood pressure (SBP) will be measured once in each arm following standard procedures. Patients will have their ankle brachial index (ABI) determined following standard procedures described by the American Heart Association³⁴. Systolic blood pressure at the ankles will

be measured at the dorsalis pedis and posterior tibialis artery using an 8 MHz doppler vascular probe and the highest blood pressure at those sites will be recorded. A ratio of highest SBP measured at the ankle divided by the SBP measured at the brachial (ABI) < 0.90 will meet the diagnostic criteria for PAD. If there are symptoms of IC, but ABI is > 0.90 than patients will perform a walking test using the Gardner protocol and if highest systolic BP at the ankle decreases by > 25 mmHg that is also diagnostic of PAD.

- 10 hour fasting venous blood sample for measurements of plasma Na⁺, K⁺, glucose, creatinine, serum insulin and urinary cGMP and creatinine. Measure BP three times and the average of those measurements will be recorded.
- will be collected for measurement of plasma potassium and creatinine/eGFR
- Women of child bearing potential will have a urine pregnancy test to verify they are not pregnant.
- Patients will perform the mini mental state evaluation to test. Patients must have a score of $\geq 23/30$ to be included in the study.

Individuals evaluated by the study physician or the main PI that meet all the inclusion and none of the exclusion criteria will continue with the following tests and procedures.

- Arterial elasticity testing using applanation tonometry in the radial artery. Patients in the supine position will have electrodes placed in their chest to record an EKG, will have a blood pressure taken and arterial pulse wave will be recorded for 30 seconds in the radial artery.
- A graded exercise testing procedure to determine pain free and maximal walking duration will be performed. Participant's blood pressure and EKG will be measured before, during and for 6 minutes following the exercise test. Contraindications outlined by the American College of Sports Medicine to perform and to stop an exercise test will be followed.
- The 6 minute walk test will be performed in a 20 meter corridor. Patients will be asked to walk as quickly as they can along the corridor for 6 minutes to cover as much distance as possible. They will be allowed to stop if they have to, but will be encouraged to continue again as soon as they are able. During the time that the participant stops walking the clock will continue to run. At the end of test the distance covered is measured.
- A Walking Impairment Questionnaire (WIQ), a 36-item short-form health survey (SF-36), and Quality of Life Questionnaire (PAD-QOL) will be given to each participant.
- Body height and weight will be measured using standard anthropometric procedures.
- Total body lean and fat mass will be determined using bioelectrical impedance from Valhalla Scientific body comp scale®.

Visit 2 (Baseline 2/Randomization)

The second screening visit will take place within 48 hours of Visit 1. The following tests and procedures will be performed:

- Women of child bearing potential will have a urine pregnancy test to verify they are not pregnant.
- MRS and fMRI will be performed in a 7 Tesla/90 cm whole-body actively shielded human

scanner.

- IDS will randomize and dispense the treatment drug or placebo.
- The subject will be given instructions on how to take the drug and will be provided a diary to keep track of any adverse events they are experiencing.
- Ambulatory blood pressure monitors using the Omron BP742N (©Omron Healthcare Inc. Lake Forest, IL) will be provided and each participant will be asked to measure and record their own arm blood pressure three times a day for the duration of the treatment period. Subjects will be asked to measure their blood pressure immediately after waking up, at noon before lunch and in the night before going to bed. Participants will be instructed on the use of the ambulatory blood pressure monitoring (ABPM) and will have a practice session.

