3.2 Laboratory Procedures

Participants will come following an 10 hour fast to provide a venous blood sample for measurements

of plasma Na^+ , K^+ , glucose, creatinine, NT-proBNP, BNP, serum insulin and also urinary cGMP and creatinine. Urine pregnancy testing will be performed at each visit on women of childbearing potential. Before the blood draw, trained personnel will measure BP three times and the average of those measurements will be recorded.

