6.4 End of Treatment

Visit 6 (End of treatment visit 1)

At the end of the 12 week treatment period, subjects will be asked to return for testing. Subjects will be asked to return within 24 hours of taking their last study pill. The following tests and procedures will be performed:

- Ankle Brachial Index (ABI)
- GXT will be done to determine pain free and maximal walking distance
- A Walking Impairment Questionnaire (WIQ), a 36-item short-form health survey (SF-36), and Quality of Life Questionnaire (PAD-QOL) will be given
- Body height and weight will be measured using standard anthropometric procedures
- Total body lean and fat mass will be determined
- Blood pressure measurement and reading of recording on the blood pressure monitor.
- Review of daily diaries for any side effects.

- Collect and assess study medication.
- Women of child bearing potential will have a urine pregnancy test to verify they are not pregnant.

Visit 7 (End of treatment visit 2)

Visit 7 will occur within 48 hours of visit 6. At that visit the following tests and procedures will be done:

- 10 hour fasting venous blood sample for measurements of plasma Na⁺, K⁺, glucose, creatinine, NT-proBNP, BNP, serum insulin and also urinary cGMP and creatinine.
- Women of child bearing potential will have a urine pregnancy test to verify they are not pregnant. The 6 minute walk test will be performed in a 20 meter corridor.
- Measure BP three times and the average of those measurements will be recorded.
- fMRI and MRS will be performed in a 7 Tesla/90 cm whole-body actively shielded human scanner.

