6.5 Follow-up Visits

Visits 8 (Follow-up, Week 6 after End of Treatment Visit)

Subjects will return 6 weeks after their treatment has ended to assess if any changes have occurred in pain free walking duration, maximal walking duration during the 6 minute walking test. Subjects will have a Walking Impairment Questionnaire (WIQ) and Quality of Life Questionnaire (PAD-QOL) administered. The presence or absence of adverse events following withdrawal of study drug will be assessed.

Schedule of Events

Schedule of Events								
	Visit 1 Screening	Visit 2 Baseline	Study Visits 3-7					Follow-up Visit 8
Time Point		Day 0	Week 2	Week 4	Week 8	Week 12	Week 12	Week 18
Time estimates	4 hours	4 hours	1 hour	1 hour	1 hour	4 hours	4 hours	45 min
Obtain Consent	x							
Ankle brachial Index	x					x		
Duplex ultrasound ¹	x							
Arterial elasticity	X					X		
Questionnaires	x					x		x
Memory test	X							
Height, weight, lean and fat mass	X					X		
Treadmill test	x					x		x
6 minute walk	x	x					x	x
MRI		x					x	
Blood draw for labs	X	x	x	x	x	x	x	
Urine test		x					x	
Blood pressure ²	x	x	x	x	x	x	x	x
Pregnancy test ³	x	x	X	X	X	X	X	X
Receive drug/placebo		x	x	x	x			
Review blood pressure records and diary			x	x	x	x		

1. Screening visit could be 5 hours long if duplex ultrasound is required, if not it will last 4 hours.
2. Visit should occur within 24 hours of last dose of drug.
3. Blood draw at screening and end of treatment visit 1 are following 10 hour fasting to assess serum: creatinine and K⁺, sodium, glucose, and serum insulin. Study visits at weeks 2, 4 and 6 are also fasting 10 hours prior to blood draw to assess: serum glucose, creatinine and potassium.
4. Duplex ultrasound will be perform only on those patients without a duplex ultrasound for the diagnosis of renal artery stenosis within the last year.
5. NIH toolbox for cognitive function.

6. The treadmill GXT test will be used to determine pain free walking distance, maximal walking distance.
7. Subjects will be instructed to measure and record their blood pressure at home, 3 times daily during the treatment period.
8. For women of childbearing potential.

7. Data Handling and Record Keeping

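### The visit lists, Schedule and laboratory section disagree on whether NT-proBNP and BNP are sampled before dosing and whether arterial elasticity is measured at Week 12

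*Combined protocol and SAP*

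**What the plan says.** **Peptides.** Section 3.2 describes a fasting panel that includes "glucose, creatinine, NT-proBNP, BNP, serum insulin and also urinary cGMP and creatinine", with no visit attached. The Visit 1 list in Section 6.1 gives nearly the same panel without the two peptides: "glucose, creatinine, serum insulin and urinary cGMP and creatinine". The Visit 2 list, which covers imaging, randomisation and dispensing, contains no blood draw. The Visit 7 list in Section 6.4 restores the peptides: "NT-proBNP, BNP, serum insulin and also urinary cGMP and creatinine". The Schedule of Events marks a blood draw at Visits 1 and 2 and at both Week 12 visits, without naming assays. Its footnote 3 begins "Blood draw at screening and end of treatment visit 1 are following 10 hour fasting to assess serum" and goes on to creatinine, potassium, "sodium, glucose, and serum insulin"; no peptide appears.

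**Arterial elasticity.** The Visit 1 list includes "Arterial elasticity testing using applanation tonometry in the radial artery". The Schedule marks elasticity at Visit 1 and at the first Week 12 visit. Neither the Visit 6 nor the Visit 7 list in Section 6.4 mentions it.

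**Use of the data.** Secondary objective 1 (Section 1.2) includes the effect of raised natriuretic peptide activity on arterial elasticity. Section 9.1 states: "Change following the 12 week clinical trial in metabolic and physiological parameters will be assessed using paired sample t-test". It also plans regressions relating metabolic and physiological changes to the walking outcomes.

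**The concern.** A paired analysis needs a value before dosing and a value at Week 12. Read on their own, the visit lists supply only the second for NT-proBNP and BNP, and only the first for arterial elasticity.

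The consequences differ. A pre-dose peptide sample cannot be taken once treatment has started. For elasticity the baseline is secure, but a missed Week 12 reading would remove the treatment comparison for a measure that the protocol names in a secondary objective. With 15 patients per group there is little room to lose either.

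**Working it through.** The plan gives no figure for this point, so the main check sets the sources side by side.

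| Source | Peptides, pre-dose | Peptides, Week 12 | Elasticity, pre-dose | Elasticity, Week 12 |
|---|---|---|---|---|
| Visit lists (6.1, 6.4) | not listed at Visit 1 or 2 | Visit 7 | Visit 1 | not listed at Visit 6 or 7 |
| Schedule grid | draws at Visits 1 and 2, assays not named | draws at both Week 12 visits, assays not named | Visit 1 | first Week 12 visit |
| Schedule footnote 3 | absent from the screening panel; Visit 2 draw not described | absent from the panel for end of treatment visit 1; Visit 7 draw not described | not covered | not covered |
| Section 3.2 | named, no visit | named, no visit | not covered | not covered |

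What can be estimated:

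- **Peptides, lists followed:** 0 pre-dose values and 1 Week 12 value per patient. Change is not computable; a randomised comparison at Week 12 is.
- **Peptides, Schedule followed:** undetermined, because the Visit 2 draw has no stated contents.
- **Elasticity, lists followed:** 1 pre-dose value and 0 Week 12 values. Neither change nor a Week 12 comparison is computable.
- **Elasticity, Schedule followed:** 1 and 1, so change is computable.
- **Urinary cGMP, lists followed:** 1 (Visit 1) and 1 (Visit 7), so change is computable.

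The precision lost without a baseline can be sized for the peptides only. Let σ² be the variance of the Week 12 value (on the log scale if transformed, as 9.1 allows), n the number per group and ρ the correlation between baseline and Week 12.

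- Week 12 values only: variance of the group difference = 2σ²/n.
- Adjusted for baseline: about 2σ²(1 − ρ²)/n, ignoring the one degree of freedom spent.
- Ratio = 1/(1 − ρ²).

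The documents give no ρ, so a range is assumed:

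- ρ = 0.5: 1/0.75 = 1.33
- ρ = 0.7: 1/0.51 = 1.96
- ρ = 0.8: 1/0.36 = 2.78

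Equivalently, 15 per group without a baseline gives the precision of 15 × (1 − ρ²) = 11.25, 7.65 or 5.4 per group with one. Against an unadjusted comparison of change scores, with equal SDs at both times, the ratio is 1/(2(1 − ρ)) = 1.00, 1.67 or 2.50. At ρ = 0.5 that method would therefore gain nothing from a baseline.

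The group size itself reproduces from Section 9.2. A difference of 278 m, SD 240 m, α = 0.05 (taken as two-sided) and power 0.85 give 14.41 by the t-test, rounded up to 15. This point does not affect it.

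**The case against.** The strongest reply is that the intended design is visible and the lists are merely abbreviated. The Schedule marks elasticity at Week 12. It also marks a blood draw and a urine test at Visit 2, and both again at the second Week 12 visit, where the Visit 7 list places the peptides and urinary cGMP. That pairing suggests that a matching panel was meant before dosing. Footnote 3 does not describe the Visit 2 draw, so its silence does not exclude peptides there. Section 3.2 treats them as part of the general panel. The Schedule also carries other items that the lists omit, such as a 6 minute walk at Visit 2.

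Much of this stands. A reader might infer that no baseline peptide sample is planned, or that no patient will have a Week 12 elasticity value. The documents do not support either. The first is unspecified rather than excluded, and the second is contradicted by the Schedule. A reader might also infer that the peptides are needed for the mechanistic objective. Secondary objective 1 does not name them. Sections 1.1.4 and 5.1 treat cGMP as a marker of natriuretic peptide activity, and urinary cGMP is listed at both time points.

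The reply does not show that the Schedule governs. No rule of precedence is given, and the Schedule is not reliable enough to assume one. It shows a Week 8 visit where Section 6.2 and its own footnote 3 say Week 6, and it puts the urine test at Visit 2 where the Visit 1 list puts urinary cGMP. Staff working from the explicit lists would order no peptides before dosing and would not repeat tonometry.

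**Conclusion.** The point holds as an internal inconsistency with a possible loss of data, not as a measure shown to be missing from the plan.

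- **NT-proBNP and BNP:** no text explicitly places a pre-dose sample. If the lists are followed, the paired analysis in 9.1 is impossible for these assays. A valid but generally less precise Week 12 comparison remains, with variance 1.33 to 2.78 times that of a baseline-adjusted one over the assumed correlations of 0.5 to 0.8. These are supporting data.
- **Arterial elasticity:** the Schedule and the end-of-treatment lists conflict. If the lists are followed, a measure named in secondary objective 1 has no treatment comparison at all. The variance ratios do not apply here, because the value at risk is the Week 12 one.

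The primary walking outcomes, the sample size, the MR measures and urinary cGMP are unaffected. The conclusion assumes that the Schedule's column positions were read correctly from the table.

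**What to change.** Before enrolment:

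1. Name NT-proBNP and BNP at one pre-dose draw that is already planned: either the Visit 1 fasting sample or the Visit 2 draw in the Schedule. If Visit 2 is chosen, add the draw to the Visit 2 list and say that it precedes the first dose.
2. Make footnote 3 and Section 3.2 agree with that choice, stating the contents of the Visit 2 and Visit 7 draws.
3. Add arterial elasticity to the Visit 6 list, so that it matches the Schedule's first Week 12 visit.
4. State whether the visit lists or the Schedule prevail where they differ.

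The cost is two assays on a baseline sample already planned, plus wording. No visit is added, and elasticity at Week 12 is already in the Schedule.
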